### **Participants**

In total, 207 participants were included in this study as 153 patients with LDH (71 females, 82 males) and 54 healthy individuals in the control group (27 females, 27 males).

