#### **Procedure**

In this study, the Analysis of the spatial and temporal gait assessment was performed using "Win-Track" gait analysis platform system (Medicapteurs, Balma, France). The dimensions of this device are 1610 mm × 652 mm × 30 mm (length/width/height); the thickness of the platform is 9 mm composed of 12288 resistive type sensors. The dimensions of these sensors are  $7.8 \times 7.8$  mm^2, and the acquisition frequency of the apparatus is up to 200 images/s enabling digitally recording the spatiotemporal information of subjects' gait based on the center of foot pressure. The participants were asked to continuously walk barefoot for ten times in their normal walking speed as straight as possible without any gait assist device on the "Win-Track" platform within the same day. The pain intensity of the patients was evaluated and recorded by a Visual Analog Scale (VAS) immediately before performing the analysis. Three flawless walking values analysis of spatiotemporal gait parameters were recorded and the arithmetic means were computed with three repetitions. Whenever they were about to take a rest, the patients were allowed to sit down on a chair. In addition, the analysis of spatiotemporal gait parameters and gait asymmetry of 59 participants who had the planned lumbar discectomy surgery, was tested before and 15 days after surgery. The analysis of the spatiotemporal gait parameters was performed on the healthy control group's participants by the same investigator using the same equipment and measurement protocol. The gait symmetry index was used to calculate the walking asymmetry.

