Official Title: Preoperative and postoperative spatiotemporal gait parameters and gait asymmetry in patients with lumbar disc herniation: a prospective, cross-sectional study

Statistical Analysis Plan:

The Statistical Package for Social Sciences (SPSS) version 23.0, was used for the all statistical analysis (SPSS Inc., Chicago, IL, USA). Normality was analyzed using the Kolmogorov Smirnov test. The Independent t-tests for parametric, or Mann-Whitney U tests for non-parametric data, was used to compare the means between the two groups for demographic characteristics, and all the spatiotemporal gait parameters. Also, kruskal-wallis test, were applied to determine differences between LDH levels groups for pain intensity. The Paired t-test and Wilcoxon test were used to analyze the spatiotemporal gait values and gait symmetry in the patients with LDH before and 15 days after surgery and between healthy controls and 15 days after surgery. A p-value of <0.05 was considered to indicate a statistically significant difference.

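### The SAP names a paired test for healthy controls versus post-operative patients, who are different people in unequal numbers (54 and 59)

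*SAP*

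**What the plan says.** The SAP is a single paragraph. The sentence at issue opens "The Paired t-test and Wilcoxon test were used to analyze the spatiotemporal gait values and gait symmetry" and then lists what those tests are applied to: "in the patients with LDH before and 15 days after surgery and between healthy controls and 15 days after surgery". One pair of tests therefore covers two contrasts:

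- patients before surgery versus the same patients 15 days after surgery;
- healthy controls versus patients 15 days after surgery.

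The protocol shows who is in each group. Under Participants it lists "54 healthy individuals in the control group (27 females, 27 males"), separate from the 153 patients. Under Procedure it describes "59 participants who had the planned lumbar discectomy surgery, was tested before and 15 days after surgery". On the controls, Procedure says only this: "The analysis of the spatiotemporal gait parameters was performed on the healthy control group's participants by the same investigator using the same equipment and measurement". This standardises the measurement; it does not match individuals.

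An earlier SAP sentence does name unpaired tests: "The Independent t-tests for parametric, or Mann-Whitney U tests for non-parametric data, was used to compare the means between the two groups". It applies them to demographic characteristics and the gait parameters. It does not say which two groups are meant, and it mentions neither the post-operative measurement nor gait symmetry. The significance rule is "A p-value of <0.05 was considered to indicate a statistically significant difference".

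**The concern.** A paired test analyses within-pair differences, so each value in one column must belong to a particular value in the other. Before and after surgery, the patient supplies that link. Between a control and an operated patient nothing does, and 59 patients cannot be paired one-to-one with 54 controls.

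This is the only contrast in the SAP that sets post-operative patients against healthy people, so any statement about how far gait or symmetry still differs from healthy values rests on it. If someone made the paired procedure run, some patients would be discarded and the pairs would come from row order. Another analyst with the same data in a different order could reach a different conclusion. If the two files shared an ordering related to gait, the error rate would also be wrong.

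**Working it through.** **Inputs.** Controls: 54 (protocol, Participants). Patients measured 15 days after surgery: 59 (protocol, Procedure). Significance level: 0.05 (SAP), taken as two-sided because sidedness is not stated. The documents give no SD, effect size or power calculation, so there is no design figure to reproduce. Differences below are in SD units and are assumed. The head counts are consistent: 71 + 82 = 153, 27 + 27 = 54, 153 + 54 = 207.

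**1. Can the test be computed?** No. Standard routines for the paired t-test and the Wilcoxon signed-rank test both stop with an error on columns of 54 and 59. Forcing them to run means dropping at least 59 − 54 = 5 patients. The t-test then has 54 − 1 = 53 degrees of freedom, against 54 + 59 − 2 = 111 for the pooled independent t-test.

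**2. The independent test.** With SD = 1 in both groups, SE = √(1/54 + 1/59) = 0.1883.

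| Observed difference | t = difference / 0.1883 | p (111 df) |
|---|---|---|
| 0.3 SD | 1.593 | 0.114 |
| 0.4 SD | 2.124 | 0.036 |
| 0.5 SD | 2.655 | 0.009 |

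**3. The same data forced into pairs.** If r is the chance correlation that an arbitrary pairing creates, SE = √(2(1 − r)/54). For a 0.4 SD difference, ignoring the small change in the mean from dropping 5 patients:

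| r | SE | t | p (53 df) |
|---|---|---|---|
| +0.27 | 0.1644 | 2.433 | 0.018 |
| 0 | 0.1925 | 2.078 | 0.043 |
| −0.27 | 0.2169 | 1.844 | 0.071 |

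The value 0.27 is about two standard deviations of a chance correlation over 54 pairs (2/√53 = 0.27). The p-value therefore moves across 0.05 on pairing alone. Which 5 patients are dropped widens the spread further.

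**4. Simulation over arbitrary pairings** (40 datasets, 400 pairings each, 54 of the 59 patients kept):

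| Observed difference | Independent p | Share of pairings with p < 0.05 |
|---|---|---|
| 0.3 SD | 0.114 | about 4% |
| 0.4 SD | 0.036 | about 61% |
| 0.5 SD | 0.009 | more than 99% |

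At 0.4 SD the central 95% of pairings gave p from about 0.011 to 0.107. A separate run of 10,000 pairings of one dataset gave 0.011 to 0.106, with 62% below 0.05.

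**5. Type I error, no true difference, nominal 5%.**

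| How the rows are lined up | Type I error |
|---|---|
| Independent t-test, no pairing | 4.8% |
| Random pairs, paired t-test | 4.8% |
| Random pairs, Wilcoxon signed-rank | 4.7% |
| Both files sorted by a variable correlated 0.2 with gait (paired t-test) | 5.4% |
| Same, correlation 0.3 | about 6% |
| Same, correlation 0.4 | about 7% |
| Same, correlation 0.6 | about 11% |
| Both columns sorted by the gait value itself | 74% (paired t-test), 77% (Wilcoxon) |

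Sorting pushes the error up because it creates a correlation within pairs. The paired formula subtracts that correlation from the variance, although the two group means remain independent. The sorting variable and its correlations are assumptions; the documents say nothing about file order. The last row is an extreme case.

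**6. The correct analysis.** The independent t-test uses all 113 people. The difference detectable with 80% power is (1.960 + 0.842) × 0.1883 = 0.53 SD.

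**The case against.** The strongest reply is that this is loose drafting. The SAP already names independent tests for gait parameters, Wilcoxon could mean the rank-sum test, and nothing shows that a paired analysis of controls against patients was ever run. That may be so, but the wording does not support it. The SAP calls the unpaired rank test Mann-Whitney U, and the paired t-test is still named for this contrast. The earlier sentence covers neither the post-operative comparison nor gait symmetry. A reader cannot tell which test stands behind a reported p-value.

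Four further points stand and limit the size of the problem:

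- Random pairing leaves the type I error near 5%. In that case the fault is an arbitrary, non-reproducible p-value and discarded patients, not inflation.
- The inflated rates need both files to share an ordering related to gait, which the documents do not indicate. At a correlation of 0.2 the effect is slight.
- The 0.4 SD example lies near the significance threshold, where pairing matters most. At 0.5 SD nearly every pairing is significant, and nothing in the documents shows which size is relevant.
- The protocol's aim does not name a return to healthy values, and a non-significant difference would not demonstrate one under either test.

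None of these supplies a pairing between 54 controls and 59 patients.

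**Conclusion.** The concern holds. The SAP names a paired procedure for two independent groups, and with 54 and 59 people it cannot be carried out as stated. If forced, its p-value depends on an arbitrary choice of pairs: at an assumed 0.4 SD difference it ranges from about 0.011 to 0.107, where the independent test gives 0.036. Type I error stays near 5% under random pairing and rises to about 7% to 11% under the assumed sorted-file scenario. These sizes assume normal data with equal SDs and are illustrative. The finding that the test is wrong rests only on the SAP's wording and the two group counts. The before-versus-after comparison in the 59 operated patients is properly paired and is not affected. The error must be fixed, because it affects the SAP's only comparison of post-operative patients with healthy controls.

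**What to change.** Split the sentence in two:

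- **Before versus 15 days after surgery, 59 operated patients:** paired t-test or Wilcoxon signed-rank test, using that full name.
- **Controls (54) versus patients 15 days after surgery (59):** independent-samples t-test (Welch's version is suitable) or Mann-Whitney U, for every gait parameter and every symmetry index, using everyone measured, with a 95% confidence interval for the difference.

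In the earlier sentence, say which two groups are meant. If controls were in fact individually matched to operated patients, state the matching rule and the number of pairs, which cannot exceed 54.

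The SAP is written in the past tense, so the sponsor should also confirm which test was run. If it was the independent test, only the wording changes. If not, this contrast has to be rerun. The cost is one sentence of SAP text and, at most, a rerun on existing data.

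### No planned contrast sets the operated patients' own pre-operative gait against healthy controls, so the plan's two gaps to normal appear to describe different sets of patients

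*SAP*

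**What the plan says.** The Protocol (Participants) defines two groups only: "In total, 207 participants were included in this study as 153 patients with LDH (71 females, 82 males) and 54 healthy individuals" as controls. Under Procedure it adds a surgical subset: "59 participants who had the planned lumbar discectomy surgery, was tested before and 15 days after surgery". No one else is described as having a day-15 measurement.

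The SAP, a single paragraph, names these contrasts for gait:

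- Independent t or Mann-Whitney U tests "to compare the means between the two groups for demographic characteristics, and all the spatiotemporal gait parameters". There is no restriction to operated patients, and gait symmetry is not listed.
- Paired t and Wilcoxon tests for the spatiotemporal values and gait symmetry "in the patients with LDH before and 15 days after surgery and between healthy controls and 15 days after surgery".

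The only stated criterion is "A p-value of <0.05 was considered to indicate a statistically significant difference". The SAP gives no n for any contrast and mentions no confidence intervals. It names neither a comparison of the operated patients' pre-operative values with controls nor a comparison of operated with non-operated patients.

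**The concern.** The SAP's title refers to both preoperative and postoperative gait, and the day-15 values are tested against healthy controls. A reader will therefore ask how far patients were from normal before surgery and how far they remained from it afterwards. The only pre-operative distance from normal that the SAP names comes from the whole LDH group. The post-operative distance comes from the operated patients alone.

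Patients selected for discectomy need not walk like the rest of the LDH group. If the two distances are read as a before/after pair, the difference between them contains selection for surgery as well as any change after surgery. The two distances also rest on different numbers of patients, so significance could be lost with no change in gait. What is at stake is any statement that gait did or did not return towards normal. The paired estimate of change is not affected.

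For gait symmetry the problem is different: there is no pre-operative distance from controls to set beside the day-15 one.

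**Working it through.** **Inputs.** From the Protocol: 153 LDH patients, 54 controls and 59 operated patients. From the SAP: significance level 0.05, taken as two-sided because sidedness is not stated. The documents give no SD, effect size, pre/post correlation or sample-size calculation. Effects below are therefore assumed values in SD units, with a common SD, and a gap means the distance from controls in the direction of worse gait.

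**1. Head counts reproduce.** 71 + 82 = 153; 27 + 27 = 54; 153 + 54 = 207, as stated.

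**2. Composition.** Assume the 59 are among the 153. Then 153 − 59 = 94 patients, or 94/153 = 61.4%, can enter the all-patient contrast but not the day-15 contrast.

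**3. Size of the discrepancy.**

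gap(all) = (59 × gap(operated) + 94 × gap(other)) / 153

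so gap(operated) − gap(all) = (94/153) × [gap(operated) − gap(other)] = 0.614 × D.

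| Assumed D (operated minus other) | Discrepancy |
|---|---|
| 0 | 0 |
| ±0.25 SD | ±0.15 SD |
| ±0.5 SD | ±0.31 SD |
| ±1.0 SD | ±0.61 SD |

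Two examples with no change at all after surgery:

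- Operated 0.8, other 0.3: gap(all) = (59 × 0.8 + 94 × 0.3)/153 = 0.49. The day-15 gap is 0.80, an apparent worsening of 0.31 SD.
- Operated 0.3, other 0.8: gap(all) = (59 × 0.3 + 94 × 0.8)/153 = 0.61. The day-15 gap is 0.30, an apparent recovery of 0.31 SD.

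**4. Unequal n.** SE = √(1/54 + 1/n).

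| Contrast | SE | Detectable gap, 80% power |
|---|---|---|
| 153 v 54 | 0.158 SD | 0.44 SD |
| 59 v 54 | 0.188 SD | 0.53 SD |

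The detectable gap is (1.96 + 0.84) × SE. For an unchanged true gap of 0.45 SD, power is 81% in the first contrast and 67% in the second.

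**5. False pattern of significant before, not significant after.** This was simulated with 40,000 runs per setting, no true change, operated and other patients alike, a true gap of 0.3 to 0.5 SD and a pre/post correlation of 0.5 to 0.9. The pattern arises in 15–20% of runs when 153 patients are used before and 59 after. It arises in 4–11% when the same 59 are used both times. These SEs and simulations treat both contrasts with controls as independent-samples comparisons.

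**The case against.** The strongest reply is that the operated patients are already covered. The paired test compares the same people before and after surgery and measures change directly. For means, the pre-operative gap also follows from what is planned: it equals the day-15 gap plus the gain. If the patients were 0.60 SD from controls at day 15 after a gain of 0.30 SD, they began 0.90 SD away and had recovered a third. With 59 pairs and a 0.30 SD gain, the paired t-test has about 62%, 83% and 95% power at assumed correlations of 0.5, 0.7 and 0.8, and 48% at 0.3.

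All of this stands. A reader might infer that the plan cannot show recovery, or that a real improvement would go unreported. The documents do not support that, because the paired test is planned and is like-for-like. What remains is narrower. The back-calculation is not planned and comes with no interval, and it does not carry over to medians or the rank tests that the SAP also allows.

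It is also fair to say that the SAP never calls the two-group test a pre-operative comparison, never sets it beside the day-15 test, and plans no statement on the share recovered. The Protocol's Aim concerns gait parameters and asymmetry in LDH, and comparing all patients with controls is a proper answer to a cross-sectional question. The problem arises only if the two gaps are read together. The title and the day-15 v control test invite that reading but do not require it.

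Finally, a reader might take the use of all 153 in the two-group test as stated fact. It is an inference: the Participants section offers no other pair of groups, but the SAP does not say so.

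**Conclusion.** The point holds in a limited form. No contrast of the operated patients' pre-operative values with controls is named, and for gait symmetry none is named for any LDH patients before surgery. For the spatiotemporal parameters, the all-patient gap and the day-15 gap are not a valid before/after pair. They would differ by 0.614 times the operated-minus-other difference even if surgery changed nothing: 0.15 SD at an assumed 0.25 SD, 0.31 SD at 0.5 SD, and zero if the subsets walk alike.

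This rests on two readings, that the two-group contrast uses all 153 patients and that the 59 are among them. The documents give no data on the size or direction of the discrepancy, so they do not support a claim that the comparison is biased by any particular amount or in a particular direction. The paired analysis of change is sound. The weakness is confined to statements about distance from, or return to, normal gait, and it can be removed cheaply.

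**What to change.** - State the n for each contrast in the SAP, and whether the 59 operated patients are among the 153.
- Add pre-operative values of the operated patients (59) v controls (54), for the spatiotemporal parameters and the symmetry index, by independent t-test or Mann-Whitney U.
- Use the same independent-samples tests for day 15 v controls. As written, the SAP assigns paired t and Wilcoxon tests to that comparison, although operated patients and healthy controls are unrelated people.
- Report the pre-operative gap, the day-15 gap and the paired change side by side with 95% CIs, and base any statement on recovery or normalisation on these three. Both gaps then have an SE of about 0.188 SD, and the composition difference disappears, given complete data on the 59. The 95% half-width is about 1.96 × 0.188 = 0.37 SD, so a non-significant day-15 gap should not be reported as normal gait.
- Show operated (59) and non-operated (94, if the 59 are a subset) patients separately at baseline.

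**Cost.** A few SAP sentences and extra table columns. No new patients or measurements are needed, since the Protocol says the operated patients were tested before surgery. The downside is more unadjusted comparisons: eight parameters on two sides plus eight symmetry indices could add up to 16 + 8 = 24. They are best presented as estimates with intervals, not as further significance tests.

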# **Study Protocol**

# **Participant Flow**

#### **INTRODUCTION**

Lumbar disc herniation (LDH) is a localized displacement of the lumbar intervertebral disc into the vertebral canal or intervertebral space, and is considered as a mechanical disorder characterized by degeneration of the disc. 1-3 Disc herniation leads to functional loss and disability in daily life activities and negatively affects the quality of life among these patients. 4-6 Depending on LDH in sprawling of pain to spine and legs, lower extremity functions, especially walking, are adversely affected and usually walk slower than their healthy individuals. 7-9 The gait parameters are important gait variables, because they can be easily evaluated and measured to obtain gait deviations and walking difficulties, make a diagnosis, determine appropriate therapy, monitor the patient's progress, determine the prognosis, and they can help in understanding the functional limitations during gait.

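### Every gait comparison in three contrasts is judged at an unadjusted p<0.05 with no primary outcome or exploratory label, and one contrast names a paired test for different people

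*SAP*

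**What the plan says.** The SAP uses independent t-tests or Mann-Whitney U tests "to compare the means between the two groups for demographic characteristics, and all the spatiotemporal gait parameters". The two groups are not named there; LDH patients and healthy controls is the natural reading. Of its paired methods, the t-test for pairs and Wilcoxon's test, the SAP says that they "were used to analyze the spatiotemporal gait values and gait symmetry in the patients with LDH before and 15 days after surgery". The same sentence then extends them to a further contrast: "and between healthy controls and 15 days after surgery". The threshold for everything is "A p-value of <0.05 was considered to indicate a statistically significant difference".

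The protocol's Main Outcome Measures section lists eight spatiotemporal parameters, each recorded for the right and left side, together with pain on a visual analogue scale and a symmetry index. None is ranked above the others. The Procedure section says "The gait symmetry index was used to calculate the walking asymmetry" but not for which parameters. The Aim singles out no parameter and no contrast.

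On group sizes, the Participants section gives 153 patients and "54 healthy individuals in the control group". The Procedure section describes "the analysis of spatiotemporal gait parameters and gait asymmetry of 59 participants who had the planned lumbar discectomy surgery", measured before and 15 days after the operation.

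**The concern.** With one blanket threshold and no ranking of outcomes, about one in 20 of the comparisons where nothing truly differs will be reported as a significant gait difference, and nothing in the plan tells the reader to treat it as possible chance. This matters most in the surgery contrasts. The Introduction says that LDH patients "usually walk slower than their healthy individuals", which gives a prior expectation for LDH against control. Neither document predicts which parameters should change by day 15, or in which direction symmetry should move.

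Two features make a chance result look stronger than it is. The parameters are closely related, so one chance difference can show up in several rows. The contrasts also overlap: the same controls serve in two of them, and the same day-15 measurements serve in two. Agreement across rows or contrasts is therefore not replication.

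The test named for controls against day-15 patients is a different kind of fault. A paired test needs a natural partner for each observation, and none exists here.

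**Working it through.** The plan states no power calculation or overall error rate, so there is no figure of its own to reproduce. The only given number is the threshold, 0.05.

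**Inputs.** Eight parameters and two sides (protocol, Main Outcome Measures); three contrasts, with symmetry named only in the two surgery contrasts (SAP); 54 controls (Participants) and 59 surgical patients (Procedure).

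**Number of gait tests.** The documents do not say whether each side is tested or which parameters receive an index.

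| Reading of the SAP | LDH vs control | Before vs after | Control vs after | Total | Total × 0.05 |
|---|---|---|---|---|---|
| One value per parameter; one index in each surgery contrast | 8 | 9 | 9 | 26 | 1.3 |
| One value per parameter; an index per parameter in the surgery contrasts | 8 | 16 | 16 | 40 | 2.0 |
| Right and left separately; an index per parameter in the surgery contrasts | 16 | 24 | 24 | 64 | 3.2 |

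The demographic and pain tests use the same threshold but are not counted.

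**Expected false positives.** With m0 tests where nothing differs, the expectation is 0.05 × m0, whatever the correlation between tests. It assumes that each test holds its 5% level, so for the third contrast it applies only once a valid test is used.
- Nothing differs anywhere: 1.3 to 3.2.
- Half of the tests truly differ: 0.05 × 13 = 0.65 to 0.05 × 32 = 1.6.
- One surgery contrast with nothing different: 0.05 × 9 = 0.45 to 0.05 × 24 = 1.2.

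**Illustration only.** The documents give no correlations, so a common correlation of 0 to 0.8 was assumed and normal test statistics were simulated, with at least 40,000 runs per setting.
- Chance of at least one p<0.05 in a contrast where nothing differs: 16 to 34% with 8 tests and 24 to 71% with 24. The upper ends are the independent case: 1 − 0.95^8 = 0.34 and 1 − 0.95^24 = 0.71.
- Expected share of false results among those called significant, with true differences set at 85% power: 5 to 7% when half of the tests differ, but 19 to 46% when only 1 of 24 does.

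**Linked parameters.** By their usual definitions (the documents give none), cadence is 60 divided by step duration in seconds, cycle duration and cycle length are sums of two steps, and velocity is cycle length over cycle duration. Four of the eight parameters are therefore nearly functions of step duration and step length.

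**The paired test.** Controls number 54 and surgical patients 59, and no matching is described. At most 54 pairs could be formed, 59 − 54 = 5 patients would be left out, and the result would depend on the arbitrary order in which people were paired.

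**The case against.** The study is observational and cross-sectional, with a descriptive aim and no stated confirmatory hypothesis. Unadjusted testing with full reporting is a defensible choice for such work. This stands, and it is why the main remedy is a label and complete reporting, not compulsory adjustment. The plan gives neither, however, and its only rule treats every p<0.05 as a significant difference.

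A reader might infer several stronger points that the documents do not support:
- *That the plan runs 24 to 72 tests.* The lower figure leaves out the symmetry that the SAP names for both surgery contrasts. The upper one adds indices to LDH against control, where the SAP does not name them.
- *That the results will contain 1.3 to 3.2 false findings, or that many of the significant results will be false.* The expectation is for a study in which nothing differs, and the Introduction expects otherwise for walking speed. The largest error rates above come from uncorrelated tests, which sits badly with parameters so closely linked. A lone true difference is also hard to picture: a change in step duration would appear in cycle duration and cadence as well.
- *That the paired-test fault adds to the multiplicity problem.* It is a separate error and would need correcting even with a single outcome.

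It could also be said that Wilcoxon might mean the rank-sum test, which suits independent groups. But the SAP names Mann-Whitney U for independent groups elsewhere and here couples Wilcoxon with the paired t-test, so the signed-rank test is the natural reading. The paired t-test is wrong for this contrast on any reading.

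**Conclusion.** The point holds in two parts of different weight. First, the test named for controls against day-15 patients is wrong as written. This follows from the documents alone and needs no assumption. Second, about 26 to 64 gait tests share an unadjusted 0.05 threshold with no primary outcome and no exploratory label. The expected 1.3 to 3.2 false positives are an upper limit for the case where nothing differs. The issue is small in a contrast where half or more parameters differ, as may be true of LDH against control, and matters more where few do. That the tests are unadjusted is inferred from the SAP's silence and its single threshold; nothing in either document contradicts it. The chance-of-any-error and false-share figures rest on assumed correlations and effect sizes and do not carry the conclusion.

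**What to change.** 1. **Correct the test.** Delete "and between healthy controls and 15 days after surgery" from the paired-test sentence of the SAP and add: *Patients 15 days after surgery are compared with healthy controls by the independent t-test or the Mann-Whitney U test.* If the paired analysis was run as written, one contrast is re-run.

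2. **Limit what a single p-value can support.** After the threshold sentence add: *All gait and symmetry comparisons are exploratory. Each is reported with an effect estimate and an unadjusted 95% CI (mean difference for t-tests, Hodges-Lehmann shift for rank tests). The sides tested, the parameters given a symmetry index and the number of tests are stated. No confirmatory conclusion is drawn from any single p<0.05, and related parameters are not counted as independent evidence.* The documents are written in the past tense, so any primary outcome chosen now should be labelled post hoc. The cost is wording, estimates and intervals; no new data are needed.

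3. **Optional.** Show Benjamini-Hochberg p-values within each contrast alongside, with the family fixed as all parameters, sides and indices actually tested, so that it cannot be chosen by result. Say that the intervals are not adjusted, since some may exclude zero where the adjusted p-value exceeds 0.05. The price is power. For a lone true difference with expected z = 3, unadjusted power is Φ(3 − 1.96) = 85%. At the threshold 0.05/m, which approximates Benjamini-Hochberg in this case, it falls to Φ(3 − 2.73) = about 60% with 8 tests and Φ(3 − 3.08) = about 47% with 24. The procedure also does not control error pooled over the three contrasts.
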